6.3. Follow-up Visits

6.3.1. Visit 11, Day 169/Week 24 (±3 Days)

- Administer PROs including: PtGA, DLQI, and EQ-5D-5L;
- Review eDiary Pruritus NRS, CCI and PSAAD completion (in selected countries) and review eDiary procedures with subject as necessary;
- Obtain vital signs including pulse rate, sitting blood pressure, respiratory rate and oral or tympanic temperature (after at least 5 minutes of rest);
- Review any changes in the subject's prior and concomitant medications and treatment information;
- Review subject use of background topical therapy as described in Section 5.9.1;
- Conduct complete physical examination;
- Conduct clinical evaluations including IGA, SCORAD, EASI and BSA (calculated in the EASI);
- Perform a single 12-lead electrocardiogram (ECG);
- Obtain samples for laboratory testing: serum chemistry, hematology (including coagulation panel), lipid profile (fasting), and urinalysis;
- Urine pregnancy test (female subjects of childbearing potential). A negative urine pregnancy test must be obtained prior to dosing with the investigational product;
- Assess need for contraception and adherence to applicable lifestyle requirements (Section 4.4). Establish willingness and ability to comply with lifestyle requirements going forward in the study;
- Assess and record any Adverse Events since the last visit.

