4.4.1. Contraception

Male subjects are not required to use contraception.

All female subjects of childbearing potential who are, in the opinion of the investigator, sexually active and at risk for pregnancy with their partner(s) must agree to use a highly effective method of contraception consistently and correctly for the duration of the active treatment period and for at least 28 days after the last dose of investigational product. The investigator or his or her designee, in consultation with the subject, will confirm that the subject has selected an appropriate method of contraception for the individual subject and her partner from the permitted list of contraception methods (see below) and will confirm that the subject has been instructed in its consistent and correct use. At time points indicated in the Schedule of Activities, the investigator or designee will inform the subject of the need to use highly effective contraception consistently and correctly and document the conversation and the subject's affirmation in the subject's chart (subjects needs to affirm their consistent and correct use of at least 1 of the selected methods of contraception). In addition, the investigator or designee will instruct the subject to call immediately if the selected contraception method is discontinued or if pregnancy is known or suspected in the subject or the partner.

Highly effective methods of contraception are those that, alone or in combination, result in a failure rate of less than 1% per year when used consistently and correctly (ie, perfect use) and include the following:

- 1. Established use of hormonal methods of contraception associated with inhibition of ovulation (eg, oral, inserted, injected, implanted, transdermal) provided the subject plans to remain on the same treatment throughout the entire study and has been using that hormonal contraceptive for an adequate period of time to ensure effectiveness.
- 2. Correctly placed copper-containing intrauterine device (IUD).
- 3. Male condom or female condom used WITH a separate spermicide product (ie, foam, gel, film, cream, or suppository). For countries where spermicide is not available or condom plus spermicide is not accepted as highly effective contraception, this option is not appropriate.
- 4. Male sterilization with absence of sperm in the post-vasectomy ejaculate.

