6. STUDY PROCEDURES

Refer to the Schedule of Activities for a detailed list of study procedures, as they should be conducted at each respective visit.

Due to possible need for PPD testing and chest radiograph, screening procedures may be performed over more than 1 visit in the 28 days prior to the Day 1 visit.

Visit windows are based on Day 1 visit. To assure consistency and reduce variability, all study visits should occur in the morning whenever possible. On days of study visits, subjects will receive their dose at the clinic during the visit.

Subjects are required to fast for at least 8 hours prior to all visits that include lipid profile panel testing (Day 1, Week 4, Week 16, Week 20 and EOS). During the fasting period, subjects should refrain from all food and liquids (water and permitted non-study medications are allowed).

ECGs will be interpreted by a central reader for all visits.

Urine pregnancy test must be performed prior to dosing with the investigational product for female subjects of childbearing potential through to the EOS visit.

Prior to attending a study visit, subjects are allowed to shower and bathe but should not moisturize or apply emollient.

Refer to Appendix 4 for guidelines on subject safety monitoring and discontinuation.

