6.2.8. Visit 9, Day 127/Week 18 (±3 Days)

- Administer PROs including PtGA;
- Obtain pre-dose vital signs including pulse rate, sitting blood pressure, respiratory rate and oral or tympanic temperature (after at least 5 minutes of rest);
- Review PSAAD daily completion (in selected countries), CCI , and Pruritus NRS completion for this visit in the eDiary;
- Review any changes in the subject's concomitant medication and treatments information;
- Check subject understanding of protocol guidance for the use of background topical therapy as described in Section 5.9.1, ensure subject adherence to background topical therapy requirements and re-educate as required;
- Conduct targeted physical examination;
- Conduct clinical evaluations including IGA, SCORAD, EASI and BSA (calculated in the EASI);
- Perform a single 12-lead electrocardiogram (ECG);
- Obtain samples for laboratory testing: serum chemistry, hematology (including coagulation panel), and urinalysis;
- Urine pregnancy test (female subjects of childbearing potential). A negative urine pregnancy test must be obtained prior to dosing with the investigational product;
- Assess need for contraception and adherence to applicable lifestyle requirements (Section 4.4). Establish willingness and ability to comply with lifestyle requirements going forward in the study;
- Review eDiary to assess completion;
- Perform drug accountability procedures;
- Administer oral investigational product and observe dosing;

• Assess and record any Adverse Events since the last visit.

6.2.9. Visit 10, Day 141/Week 20 (±3 Days) End of Treatment or Early Termination Visit

- Administer PROs including PtGA, DLQI, EQ-5D-5L, HADS, and POEM;
- Obtain weight;
- Obtain pre-dose vital signs including pulse rate, sitting blood pressure, respiratory rate and oral or tympanic temperature (after at least 5 minutes of rest);
- Review eDiary Pruritus NRS, CCI , and PSAAD completion (in selected countries) and review eDiary procedures with subject as necessary;
- Review any changes in the subject's prior and concomitant medications and treatment information;
- Check subject understanding of protocol guidance for the use of background topical therapy as described in Section 5.9.1, ensure subject adherence to background topical therapy requirements and re-educate as required;
- Conduct complete physical examination;
- Conduct clinical evaluations including, IGA, SCORAD, EASI and BSA (calculated in the EASI);

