- Perform a single 12-lead electrocardiogram (ECG);
- Obtain samples for laboratory testing: serum chemistry, hematology (including coagulation panel), lipid profile (fasting), and urinalysis;

- For China, Republic of Korea, Taiwan, and Japan only: For subjects who had HBV DNA testing at Screening, collect blood sample for repeat HBV DNA testing, as appropriate;
- Urine pregnancy test (female subjects of childbearing potential). A negative urine pregnancy test must be obtained prior to dosing with the investigational product;
- Assess need for contraception and adherence to applicable lifestyle requirements (Section 4.4). Establish willingness and ability to comply with lifestyle requirements going forward in the study;
- Review eDiary to assess completion;

- Perform drug accountability procedures;
- Administer oral investigational product and observe dosing;
- Assess and record any Adverse Events since the last visit;
- Subjects who complete the trial to this visit will be assessed for eligibility for participation in long-term extension study B7451015. Subjects who are not eligible or are not interested are to continue to Visit 11 (see Section 6.3.1).

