6.4. Subject Withdrawal

Ongoing safety concern at the time of subject withdrawal from the study:

If a subject has a clinically significant, treatment-emergent, abnormality at the time of withdrawal from the study, the Pfizer Medical Monitor (or designee) should be notified and every effort should be made to arrange follow-up evaluations at appropriate intervals to document the course of the abnormality. All abnormal laboratory events of clinical significance should be followed until the laboratory values have returned to normal or baseline levels or are deemed clinically stable. Follow-up for abnormal laboratory findings and adverse events by the investigator is required until the event or its sequelae resolve or stabilize at a level acceptable to the investigator, and Pfizer concurs with that assessment. Refer to Appendix 4 for Guidelines for Monitoring and Discontinuation.

Withdrawal of consent:

Subjects who request to discontinue receipt of study treatment will remain in the study. If this request occurs at a scheduled visit, an end of treatment visit should be performed and the subject should enter into the follow-up period, with an end of study visit scheduled for 4 weeks after the end of treatment visit. If the request occurs outside of a scheduled visit (eg, via telephone contact) the subject should be scheduled to return to site for an end of treatment visit within one week, and the subject should enter into the follow-up period, with an end of study visit scheduled for 4 weeks after the end of treatment visit.

The only exception to this is when a subject specifically withdraws consent for any further contact with him or her or persons previously authorized by the subject to provide this information. Subjects should notify the investigator in writing of the decision to withdraw consent from future follow-up, whenever possible. The withdrawal of consent should be explained in detail in the medical records by the investigator, as to whether the withdrawal is only from further receipt of investigational product or also from study procedures and/or posttreatment study follow-up, and entered on the appropriate CRF page. In the event that vital status (whether the subject is alive or dead) is being measured, publicly available information should be used to determine vital status only as appropriately directed in accordance with local law.

Lost to follow-up:

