8.1.4. Time Period for Collecting AE/SAE Information

The time period for actively eliciting and collecting AEs and SAEs ("active collection period") for each subject begins from the time the subject provides informed consent, which is obtained before the subject's participation in the study (ie, before undergoing any study-related procedure and/or receiving investigational product), through and including a minimum of 28 calendar days; except as indicated below after the last administration of the investigational product.

For subjects who are screen failures, the active collection period ends when screen failure status is determined.

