3.5.1. Adverse Events

An adverse event will be considered a Treatment-Emergent Adverse Event (TEAE) if the event started during the effective duration of treatment. All events that start on or after the first dosing day and time / start time, if collected, but before the last dose plus the lag time (28 days) will be flagged as TEAEs. The algorithm will not consider any events that started prior to the first dose date.

A 3-tier approach will be used to summarize AEs. Under this approach, AEs are classified into one of 3 tiers. Different analyses will be performed for different tiers (See [Section 6.9.1](#)).

Tier-1 events: These are pre-specified events of clinical importance and are maintained in a list in the product's Safety Review Plan.

Tier-2 events: These are events that are not Tier-1 but are "common". A MedDRA Preferred Term (PT) is defined as a Tier-2 event if there are at least 4 subjects with an event in any treatment group.

Tier-3 events: These are events that are neither Tier-1 nor Tier-2 events.

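### The Visit 11 window lets the last scheduled adverse-event query fall before the protocol's 28-day minimum collection period has elapsed, and no later contact is planned

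*Protocol*

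**What the plan says.** **Collection period.** Protocol Section 8.1.4 has AEs and SAEs actively elicited from consent "through and including a minimum of 28 calendar days" after the last administration of investigational product. The only exception it then gives is for screen failures. After that period, Section 8.1.4.1 relies on SAEs that the investigator happens to learn of. SAP Section 3.5.1 flags an event as treatment-emergent if it starts on or after first dosing but "before the last dose plus the lag time (28 days").

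**Last dose.** The end-of-treatment visit is "6.2.9. Visit 10, Day 141/Week 20 (±3 Days) End of Treatment or Early Termination Visit". Its procedure list includes "Administer oral investigational product and observe dosing", so a completer's last oral dose is given at that visit.

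**Last contact.** The follow-up visit is "6.3.1. Visit 11, Day 169/Week 24 (±3 Days"). It is the final column of the Schedule of Activities, and no call or visit follows it. It serves completers who do not enter the extension, and subjects who stop treatment early.

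**Two anchors.** Section 6 says "Visit windows are based on Day 1 visit". The Schedule of Activities header labels the same visit as four weeks after end of treatment or early termination, and Section 6.4 places it in follow-up "with an end of study visit scheduled for 4 weeks after the end of treatment visit". Section 6.4 also allows the end-of-treatment visit to take place up to 1 week after the last dose when treatment is stopped early.

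**The concern.** The collection rule sets a floor counted from the last dose. The visit schedule sets a target with a tolerance on both sides, and that target sits exactly on the floor. Any use of the early half of the window then puts the final AE query short of 28 days.

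The missed days lie inside the SAP's treatment-emergent period. An event starting in them belongs in the safety tables by definition, but no scheduled contact asks about it. The subjects concerned have no extension visit to pick it up. They include everyone taken off treatment under the Appendix 4 discontinuation criteria, for whom late safety follow-up matters most. For a subject who withdrew with no drug dispensed at Week 16, SAP Appendix 2 puts all available data into the Week 16 Analysis, on which the final study report rests. The gap is therefore not confined to the supplemental report.

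**Working it through.** Day arithmetic is enough here. The day of the last dose is counted as day 0.

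**Inputs**
- Visit 10 target Day 141, ±3: Days 138 to 144 (Section 6.2.9).
- Visit 11 target Day 169, ±3: Days 166 to 172 (Section 6.3.1).
- Last oral dose on the day of Visit 10 for completers (Section 6.2.9).
- Required active collection: at least 28 days after the last dose (Section 8.1.4).

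**The plan's own figure.** 169 − 141 = 28 days. This matches the stated four weeks and leaves no margin.

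**Completers, Visit 11 timed from the end-of-treatment visit.** Gap = 28 ± 3, so 25 to 31 days. The earliest visit is 28 − 25 = 3 days short.

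**Completers, both windows timed from Day 1.** Gap = (169 + b) − (141 + a) = 28 + b − a, with a and b each from −3 to +3.
- Shortest: 166 − 144 = 22 days, which is 6 short.
- Longest: 172 − 138 = 34 days.
- With Visit 10 on its target day, the shortest is 166 − 141 = 25 days.

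The 7 × 7 = 49 permitted day pairs distribute as follows:

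| Gap (days) | 22 | 23 | 24 | 25 | 26 | 27 | 28 or more |
|---|---|---|---|---|---|---|---|
| Pairs | 1 | 2 | 3 | 4 | 5 | 6 | 28 |

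So 1 + 2 + 3 + 4 + 5 + 6 = 21 of 49 pairs (43%) fall short. The median shortfall among those 21 is 2 days. With the end-of-treatment anchor, 3 of 7 permitted days (43%) fall short. These are counts of permitted combinations. They become probabilities only if visits spread evenly over their windows, which the documents do not say.

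**Sensitivity to the last dose.** If the last dose were taken the day before Visit 10, the minima would be 26 days (end-of-treatment anchor) and 23 days (Day 1 anchor), both still short.

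**Early stoppers.** A Day 1 anchor cannot apply, so Visit 11 is timed from the end-of-treatment visit. If that visit is d days after the last dose (0 to 7), the earliest Visit 11 is d + 25 days after it:

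| d | 0 | 1 | 2 | 3 | 4 to 7 |
|---|---|---|---|---|---|
| Earliest Visit 11 | 25 | 26 | 27 | 28 | 29 to 32 |

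The shortfall is possible only for d of 0, 1 or 2.

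**The case against.** **Section 8.1.4 binds sites on its own terms.** A reader might infer that a fully compliant site ends collection early. That goes too far. A site that stops asking at day 25 meets the visit window but not Section 8.1.4, and SAEs learned of later remain reportable. This stands. What is missing is any scheduled contact by which a site would meet the duty.

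**Twenty-two days is a corner case.** It needs the Day 1 anchor and 1 of 49 day pairs. The text specific to Visit 11 times it from the end of treatment, where the minimum is 25. This also stands, so 22 should not be read as typical.

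**Contraception.** Section 4.4.1 requires it "for at least 28 days after the last dose of investigational product", and a reader might infer a second contradiction. There is none: the duty is the subject's own and continues after the visit. Nor does it help to argue that Visit 11 could miss a late conception, because a test on day 28 could miss it too. Pregnancies found after discontinuation come under the exposure-during-pregnancy reporting in Section 8.4.3.1.

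**The consequence is probably small.** Section 1.3 gives a mean terminal half-life of 1.9 to 5.0 hours. Twenty-two days is 528 hours, or more than 100 half-lives at 5 hours. In the dupilumab arm the last injection is at Week 14 (Day 99), so Day 166 is 67 days later. SAP Section 6.10 puts Week 24 data in listings only unless otherwise noted. All of this limits the importance. It does not exclude delayed effects, and it does not reconcile the two rules.

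**Conclusion.** The point holds as an inconsistency between the visit schedule and the AE-collection rule. For completers outside the extension, the schedule permits the final AE query 3 days before the 28-day minimum when Visit 11 is timed from the end of treatment, and up to 6 days before it when timed from Day 1. For early stoppers, the shortfall is at most 3 days and needs an end-of-treatment visit within 2 days of the last dose. Subjects who move to the extension are not affected by the Visit 11 timing.

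The completer figures assume that the last oral dose is the one observed at Visit 10. How often a shortfall would occur cannot be told from the documents.

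Severity is minor. The documents do not support an inference that any primary or key secondary result is at risk, that collection is formally cut to 22 days, or that the contraception rule is breached. SAP Section 3.5.1 classifies events and sets no collection duty of its own. It matters here because it shows that the uncovered days fall within the analysis definition.

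**What to change.** State one anchor for Visit 11, the actual last dose of investigational product, with a one-sided window of the present width: for example, 28 days after the last dose, 0 to +6 days. That is still seven permitted days, and none falls before day 28. Make the change in the Schedule of Activities (header and window row), in Sections 6, 6.3.1 and 6.4, and in the copy of the schedule in SAP Appendix 8, so that all agree with Section 8.1.4.

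Section 6.4 needs rewording as well as a new number. If an early stopper's end-of-treatment visit is 7 days after the last dose, the new window falls 28 − 7 = 21 to 34 − 7 = 27 days after that visit, not four weeks after it. The SAP Appendix 2 window for Week 24 is open-ended from Day 156 and needs no change.

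The cost is a text change, with no added visit or procedure. Some subjects finish a few days later: compared with the end-of-treatment anchor, a completer's window moves from 25–31 to 28–34 days. If the present window is kept, the alternative is a telephone AE query on or after day 28 whenever Visit 11 falls earlier. That does add a contact.

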6.4. Subject Withdrawal

Ongoing safety concern at the time of subject withdrawal from the study:

If a subject has a clinically significant, treatment-emergent, abnormality at the time of withdrawal from the study, the Pfizer Medical Monitor (or designee) should be notified and every effort should be made to arrange follow-up evaluations at appropriate intervals to document the course of the abnormality. All abnormal laboratory events of clinical significance should be followed until the laboratory values have returned to normal or baseline levels or are deemed clinically stable. Follow-up for abnormal laboratory findings and adverse events by the investigator is required until the event or its sequelae resolve or stabilize at a level acceptable to the investigator, and Pfizer concurs with that assessment. Refer to Appendix 4 for Guidelines for Monitoring and Discontinuation.

Withdrawal of consent:

Subjects who request to discontinue receipt of study treatment will remain in the study. If this request occurs at a scheduled visit, an end of treatment visit should be performed and the subject should enter into the follow-up period, with an end of study visit scheduled for 4 weeks after the end of treatment visit. If the request occurs outside of a scheduled visit (eg, via telephone contact) the subject should be scheduled to return to site for an end of treatment visit within one week, and the subject should enter into the follow-up period, with an end of study visit scheduled for 4 weeks after the end of treatment visit.

The only exception to this is when a subject specifically withdraws consent for any further contact with him or her or persons previously authorized by the subject to provide this information. Subjects should notify the investigator in writing of the decision to withdraw consent from future follow-up, whenever possible. The withdrawal of consent should be explained in detail in the medical records by the investigator, as to whether the withdrawal is only from further receipt of investigational product or also from study procedures and/or posttreatment study follow-up, and entered on the appropriate CRF page. In the event that vital status (whether the subject is alive or dead) is being measured, publicly available information should be used to determine vital status only as appropriately directed in accordance with local law.

Lost to follow-up:

All reasonable efforts must be made to locate subjects to determine and report their ongoing status. This includes follow-up with persons authorized by the subject as noted above. Lost to follow-up is defined by the inability to reach the subject after a minimum of 2 documented phone calls, faxes, or e-mails as well as lack of response by the subject to 1 registered mail letter. All attempts should be documented in the subject's medical records. If it is determined that the subject has died, the site will use locally permissible methods to obtain the date and cause of death. If the investigator's use of a third-party representative to assist in the follow-up portion of the study has been included in the subject's informed consent, then the investigator may use a sponsor-retained third-party representative to assist site staff with obtaining the subject's contact information or other public vital status data necessary to

complete the follow-up portion of the study. The site staff and representative will consult publicly available sources, such as public health registries and databases, in order to obtain updated contact information. If, after all attempts, the subject remains lost to follow-up, then the last-known-alive date as determined by the investigator should be reported and documented in the subject's medical records.

Subjects may withdraw from the study at any time at their own request, or they may be withdrawn at any time at the discretion of the investigator or sponsor for safety (see also the Withdrawal From the Study Due to Adverse Events section) or behavioral reasons, or the inability of the subject to comply with the protocol-required schedule of study visits or procedures at a given study site. Subjects that discontinue study treatment will remain in the study and must have their end of treatment visit within 1 week after their last dose, and will then enter the 4-week follow-up period. See Appendix 4 for Guidelines for Monitoring and Discontinuation.

If a subject does not return for a scheduled visit, every effort should be made to contact the subject. All attempts to contact the subject and information received during contact attempts must be documented in the subject's medical record. In any circumstance, every effort should be made to document subject outcome, if possible. The investigator should inquire about the reason for withdrawal, request that the subject return all unused investigational product(s), request that the subject return for a final visit, if applicable, and follow up with the subject regarding any unresolved AEs.

If the subject withdraws from the study, and also withdraws consent for disclosure of future information, no further evaluations should be performed, and no additional data should be collected. The sponsor may retain and continue to use any data collected before such withdrawal of consent.

